mood symptoms. It is possible for this prediction to be supported in the absence of a general association between treatment and mood symptoms (Prediction 1), which would suggest that these metabolic changes impact clinical outcome but are not induced by omega-3 fatty acids (i.e., they are a treatment-independent marker for clinical improvement). If both components of Prediction 4 are supported, it will be of further interest to assess the extent of mediation: If the direct (i.e., residual) treatment effect is not statistically significant, the data are consistent with *complete mediation* (i.e., the treatment effect on mood is fully accounted for by the intermediate effect on metabolite levels). If other effects of treatment on mood symptoms not specified by this model exist, the direct (i.e., residual) treatment effect may remain significant and the data would be said to support *partial mediation*. Path analysis⁸², which for linear models is a decomposition of the linear covariance matrix of the variables, will be used to analyze the fit of the proposed mediation model to our data. Path analysis can be thought of as an extension of linear regression to systems of simultaneous linear regression equations. This allows for the same variable to serve as an independent variable in some of the regressions and a dependent variable in others. In this study, changes in metabolite levels assume both roles: They are dependent variables in prediction 4(a) and independent variables in prediction 5(a). CDRS-R scores as well as other pilot mood measures will serve as the final outcome measures, with changes in metabolite levels as mediators and treatment group as an independent variable. Estimation of all the path coefficients, along with bootstrap computation of associated standard errors and significance levels (adjusted $\alpha=0.017$ to control for multiple testing) will be carried out using the SAS macros,⁷⁸ which are available for download at [http://www.comm.ohio-state.edu/ahayes/SPSS% 20programs/indirect.sas](http://www.comm.ohio-state.edu/ahayes/SPSS%20programs/indirect.sas). We also will examine the effect of metabolite changes on behavioral symptoms (ADHD-RS scores), functional ratings and the pilot mood burden scale on these models in a set of expanded path models. The Bayesian Information Criterion (BIC) will be used to assess the goodness of fit of different path models to the data. This model comparison statistics combines the likelihood of the data with a penalty term that adjusted for the number of parameters used to fit the data. This statistic can be used to rank the mediation model against simpler models where one or both of the components of Prediction 4 are assumed to be absent, or where these paths are supported with respect to some metabolites but not others. Another comparison of interest (though secondary to our aims) is to compare the full path model (which shows partial mediation, since a path representing residual treatment effect is included) to a complete mediation model which does not have a direct path from treatment to mood symptoms (implying that the correlation between treatment and mood symptoms, after accounting for metabolite levels, is zero). If both of the paths involving metabolite levels are null, but the correlation between treatment and mood symptoms is significant, the path model reduces to simple linear regression (i.e., a t-test, since the independent variable is binary). Comparison of overall model fit with BIC is important since a model in which the paths for predictions 4(a) and 4(b) fall somewhat close to significance, (e.g., $p=0.05$ for each path) may still give a better overall fit to the data than a model that omits both of these paths.

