
Prediction 5: The relationship between changes in RBC omega-3 fatty acid levels and changes in mood symptoms is mediated by metabolite changes. This prediction is similar to Prediction 4, but more precisely specifies the mechanism by which omega-3 fatty acids are hypothesized to influence mood symptoms. Specifically, changes in RBC omega-3 fatty acid levels (which are taken to be a surrogate for omega-3 levels in the brain) are predicted to be associated with changes in metabolite levels, which will in turn influence mood symptoms. These analyses will be performed in the subsample of subjects who are randomized to treatment with omega-3 fatty acids. Prediction 5(a) is that

increases in RBC omega-3 fatty acid levels will lead to decreases in Glu and mI levels and increases in NAA levels within VLPFC and ACC. While the mediation model of Prediction 4 specifies treatment assignment as the independent variable, in this set of models we treat RBC omega-3 levels within the omega-3 treated group as the predictor variable (although all subjects will receive the same nominal treatment they will display variation in their measured omega-3 levels due to differences in metabolism, diet and treatment compliance). Prediction 5(b) is that decreases in Glu and mI levels in VLPFC and ACC, and increases in NAA in VLPFC and ACC, will lead to decreases in mood symptoms. This component is the same as Prediction 4(b), but focused on the omega-3 treated group. While the metabolite level changes were dependent variables in Prediction 5(a), in Prediction 5(b) they are independent predictors of mood symptoms. As above, the covariance of these variables will be decomposed using path analysis, with $\alpha=0.017$ used to assess significance of individual paths, and BIC used to rank competing models (e.g., simplified models with one or more paths deleted).

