Exploratory analyses: In order to examine the potential impact of missing data on analyses, we will determine whether there are significant differences in demographic or clinical variables between completers and non-completers within and between treatment groups. We will examine the effect of any variables that differ and adjust analyses as necessary. Additionally, we will perform sensitivity analyses to determine whether missing data in the form of unknown changes in neurophysiologic parameters influenced our findings. Specifically, in regression analyses where change in mood symptom rating is predicted from change in a neurophysiologic and biological measure four analyses will be performed: No imputation (only available data is used), group mean imputation (for each missing change value, the mean change value of the corresponding treatment group will be substituted), and zero substitution (a change of zero is assumed for each missing change value). Additionally, associations between baseline neurophysiologic measures and subsequent “missingness” will be evaluated using regression analyses, predicting “missingness” on later scans from the baseline value, change in symptom ratings, and treatment assignment). We will also compare baseline neurometabolite levels (NAA, mI, Glu, Cho, and Cr) within each VOI in the subjects with a demographically matched subgroup of healthy control adolescents from the BITREC in order to determine the direction of any changes that occur in the subjects (i.e. whether they normalize following treatment with omega-3 fatty acids) using a separate regression for each VOI, with neurometabolite levels as the dependent variables and group (baseline at-risk adolescents with MDD vs. healthy controls) as the independent variable. Additionally, we will use multiple regression models to analyze associations between baseline neurochemical levels and omega-3 blood levels with change in mood and behavior rating in each treatment group. The treatment by change in rating scale interaction term will be the primary measure of interest. We will also explore the effects of nicotine use, illness duration, and change in behavioral, functional, and pilot mood burden measures on changes in omega-3 fatty acid levels and neurometabolite levels. Because these exploratory analyses are hypothesis-generating secondary analyses, we will use a standard 0.05 significance level as a threshold for interpreting interactions that may warrant further study. For all analyses, we will visually inspect plots of data points to identify outliers and will examine their clinical and neurophysiologic characteristics to determine their relevance to understanding treatment effects. We will examine the impact of clinical factors (e.g. ADHD and other co-occurring diagnoses) that may contribute to neurophysiologic, RBC fatty acid levels or efficacy findings as effect moderators. We will also conduct analyses of treatment group as a possible *moderator* of the association between changes in metabolite levels and mood symptoms. Moderator models allow the strength (possibly

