Patients: This is a 12-week double-blind randomized investigation of omega-3 fatty acid (N=30) vs. placebo (N=30) for the treatment of major depressive disorder and depressive disorder NOS in adolescents (N_{Total}=60). Patient selection will be done by research staff in consultation with and with permission from the PI. Inclusion/Exclusion criteria are found below (see F., 3.).

Healthy Controls: Although we will not recruit healthy subjects for the proposed study, they are recruited (n=40) already for BITREC Project 3 and undergo an initial ¹H-MRS scan. Therefore, we will be able to interpret the direction of neurobiological changes in at-risk adolescents (i.e., whether patient values are changing toward or away from those of healthy adolescents).

2. Estimated sample size: We propose to randomize 30 subjects per treatment group, for a total of 60 subjects at the University of Cincinnati. As this is an investigator-initiated protocol, there are no other sites associated with this submission.

Based on our prior studies, we estimate that approximately 25% of patients will either discontinue study participation prior to completing study procedures or will not have usable MRS data. For the power calculations described, we considered medium to large effect sizes of $d > 0.6-0.8$ to be clinically relevant.⁷⁹

3. Description of Inclusion/Exclusion Criteria

Inclusion Criterion:

- Ages 9 -21 years old.
- At least one biological parent with bipolar I disorder.
- Meets DSM-IV-TR⁸⁰ criteria for major depressive disorder (MDD) or Depressive Disorder NOS at screening as determined by the Washington University at St. Louis Kiddie Schedule for Affective Disorders and Schizophrenia, WASH-U-KSADS;⁸¹
- Childhood Depression Rating Scale-Revised Version^{40,41} (CDRS-R) scores ≥ 28 at screening and baseline.
- Fluent in English.
- Provision of written informed consent/assent as previously described.
- Agrees to use one of the following method of birth control: complete abstinence from sexual intercourse, barrier (diaphragm or condom), or oral/injectable contraceptive.

Exclusion Criterion:

- Contraindication to an MRI scan (e.g., metal clips, braces or claustrophobia).
- Mood symptoms resulting from acute medical illness or acute intoxication or withdrawal from drugs or alcohol as determined by careful medical evaluation or rapid symptom resolution.
- Psychotic symptoms (i.e., hallucinations or delusions).
- Any lifetime history of a manic or hypomanic episode.

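### The missing-scan sensitivity plan announces four analyses but lists three, and its two substitutions are weak tests of whether missing scans influenced the metabolite-mood slope

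*Combined protocol and SAP*

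**What the plan says.** The passage is the paragraph headed Exploratory analyses in section E.b of the combined protocol and SAP. It sets out sensitivity analyses for unknown changes in neurophysiologic parameters, to see whether missing data affected the findings. They apply to regressions in which "change in mood symptom rating is predicted from change in a neurophysiologic and biological measure".

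- **Count and first items:** "four analyses will be performed: No imputation (only available data is used), group mean imputation".
- **Arm-mean rule:** "for each missing change value, the mean change value of the corresponding treatment group will be substituted".
- **Zero rule:** "a change of zero is assumed for each missing change value".

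No fourth analysis follows. The next sentence adds regressions that predict missingness from the baseline value, symptom change and treatment. Their outcome is different, so they are not naturally the fourth item.

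The sensitivity sentence names no treatment term, but the main models of this kind deal with treatment:

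- Prediction 4 specifies a path model "with changes in metabolite levels as mediators and treatment group as an independent variable".
- For Prediction 5: "These analyses will be performed in the subsample of subjects who are randomized to treatment with omega-3 fatty acids".
- The moderator ANCOVA contains treatment, metabolite change and their interaction.

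Section F.2 expects that "approximately 25% of patients will either discontinue study participation prior to completing study procedures or will not have usable MRS data".

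**The concern.** A sensitivity analysis for missing data is useful only if it could give a different answer when the missing-data assumption fails. An arm-mean fill places every unscanned patient at the centre of the observed metabolite changes in that arm. Those patients then carry no weight in a within-arm slope. Agreement with the available-case slope follows from algebra, yet it could be reported as robustness.

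A zero fill does move the slope, but under the plan's own hypothesis part of that movement comes from the fill itself. Neither fill uses mood to predict the missing metabolite change, although CDRS-R and YMRS are scheduled at every visit.

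This matters because mood-related missingness is plausible. The Safety Monitoring section withdraws patients with sustained CDRS-R or YMRS worsening, or with increased suicidality. Mediation is the subject of Specific Aim 2. The unnamed fourth analysis also leaves a choice that could be made after the data are seen.

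**Working it through.** **Count.** Announced: 4. Listed: no imputation, arm mean, zero = 3. The stated figure is not reproduced.

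**Inputs from the documents.** 30 per arm, 60 in total; about 25% missing or unusable (F.2), so 60 x 0.75 = 45 usable scans. The documents give no mean, SD or slope for metabolite change. All slopes and shifts below are therefore assumptions, with shifts in SD units.

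**Arm-mean fill.** With treatment in the model, the slope is

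b = sum over arms and patients of (x - arm mean of x) y / sum over arms and patients of (x - arm mean of x)^2.

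A filled patient has x equal to the observed arm mean. The arm mean is unchanged and the patient adds zero to both sums, so b is unchanged whatever caused the missingness. The same holds in one arm alone and with the treatment interaction. It requires that all mediators in the model are missing together and that there are no other covariates. Single simulated datasets (30 per arm, 25% missing) show both the identity and its limits:

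| Model and missingness | Available-case slope | Arm-mean slope |
|---|---|---|
| Treatment in model, random | 0.509018 | 0.509018 |
| Treatment in model, depends on mood change | 0.184032 | 0.184032 |
| Treatment in model, depends on metabolite change | 0.258096 | 0.258096 |
| Pooled, no treatment term, random | 0.495 | 0.432 |
| Treatment plus a correlated covariate, random | 0.402 | 0.384 |

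The identity covers the slope only. In the second row the standard error is 0.124 for available-case and 0.151 after filling.

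**Zero fill, missing completely at random.** Let m be the fraction missing and r the mean change divided by its SD.

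- Within one arm, the slope is multiplied by 1/(1 + m r^2).
- With two equal arms, treatment in the model and mean change only in the omega-3 arm, only that arm's sum of squares is inflated, so the factor is 1/(1 + m r^2/2).

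With m = 0.25 and an assumed true slope of 0.50:

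- r = 0: 0.50/1 = 0.50 (no bias)
- r = 0.5: 0.50/1.03125 = 0.485
- r = 0.8: 0.50/1.08 = 0.463
- r = 1.5: 0.50/1.28125 = 0.390

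Simulation gives about 0.49, 0.46 to 0.47 and 0.39 for the last three. In one arm at r = 1, the factor is 0.87, 0.80 and 0.74 for 15%, 25% and 35% missing.

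**Missingness that depends on mood change.** With about a quarter missing and a true slope of 0.50, simulated available-case and arm-mean slopes coincide at about 0.42 to 0.44, while multiple imputation using mood change gives about 0.47 to 0.50. Under a harsher mechanism (true slope 0.40; the quarter of patients with the highest noisy mood-change score lose their scans), both average about 0.27. The size depends on the assumed mechanism; the coincidence does not.

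**The case against.** Several stronger readings are tempting, and the documents do not support them.

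- **That the whole result must agree.** Only the slope is fixed, and only in the models described. The sensitivity sentence names no treatment term, and the same paragraph allows adjustment for variables that differ between completers and non-completers, which would break the identity. The direct treatment effect, used under Prediction 4 to separate complete from partial mediation, can also change. In one simulation with mood-dependent missingness (assumed slope 0.5, shift 0.8 SD, direct effect 0.2), its mean went from 0.18 to 0.26, and slope significance at 0.017 flipped in 8% of datasets.
- **That zero filling is always wrong.** It has no bias under random missingness when mean change is zero, and it is correct if unscanned patients truly did not change. With mood-dependent missingness and zero mean change, it was nearer the truth than available-case (0.32 against 0.26, truth 0.40); with a 0.5 SD shift in one arm it was worse (0.20 against 0.27). It is a crude, single not-at-random scenario.
- **That false positives rise on the treatment-to-metabolite path.** The substitutions are specified only for regressions with mood change as the outcome, so this path is not submitted to them.
- **That mood-dependent missingness is established.** The 25% mixes dropout with unusable spectra, and section H pays for a scan at week 12 or termination, so some withdrawn patients may still be scanned.
- **That the plan ignores the mechanism, or that the unlisted analysis was meant to be multiple imputation.** The completer comparisons and missingness regressions examine dependence on observed data, though they cannot exclude dependence on unobserved values. The text does not show what the fourth analysis was.

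It is also fair that these are hypothesis-generating checks in a pilot study. That limits the consequence; it does not make the arm-mean comparison of slopes informative.

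**Conclusion.** The concern holds in a limited form. The count mismatch is certain from the text. In the plan's treatment-adjusted, single-arm and interaction models, arm-mean filling cannot show whether missing scans influenced the slope. That is exact, given no other covariates and mediators missing together. Zero filling attenuates the slope under random missingness if the predicted metabolite change occurs: by about 3% (0.485/0.50), 7% (0.463/0.50) and 22% (0.390/0.50) at assumed omega-3 shifts of 0.5, 0.8 and 1.5 SD, and not at all at zero shift. Under mood-dependent missingness, which is plausible but not demonstrated, the available-case and arm-mean slopes share the same bias.

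The magnitudes are illustrative because the documents give no distribution of metabolite change. The impact is limited to the exploratory sensitivity checks on the mediator analyses under Aim 2; the efficacy MMRM is unaffected.

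**What to change.** In the Exploratory analyses paragraph:

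1. Name the missing analysis or change the count to three.
2. State that treatment is in the sensitivity model, and list any other covariates.
3. Add multiple imputation of metabolite change from arm, baseline metabolite and a few mood summaries, for example baseline and last observed CDRS-R and YMRS. Specify how it is combined with the bootstrap path analysis.
4. Add a delta-shift version over a stated range, to cover missingness that depends on the unobserved metabolite change.
5. Keep the arm-mean and zero substitutions only as descriptive, with a note that agreement of the arm-mean slope is not evidence of robustness.

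The cost is revised wording and some extra programming. The imputation model must stay small: baseline to week 12 is 13 visits, and 13 x 2 scales = 26 mood scores, too many predictors for about 45 scans. Combining imputation with the bootstrap also needs care.

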- Any initiated psychotherapy within 2 months prior to the screening visit, or plans to initiate psychotherapy during study participation. Adolescents who present with their current depressive episode despite longer-term psychotherapy (i.e., >2 months) may be included. For participants who enter the study on psychotherapy, the type and frequency of therapy will remain constant during the study.

4. Inclusion of children, women, and minorities: The proposed study exclusively involves children ages 9-21 years old. As previously noted, we are not including children below age 9 years as it is not possible to control for age-related differences in brain development with the number of subjects we are proposing to study. We expect to enroll equal numbers of females and males in this study consistent with the epidemiology of offspring of parents with bipolar I disorder and of the local Cincinnati community (52.8% women and 47.2% men). Efforts will be made to have the study population reflect the ethnic distribution of the catchment area covered by the University of Cincinnati, which serves a population that is approximately 50% White, 45% African-American and 2% Asian, and 3% other racial groups, and the local Cincinnati area, which according to the 2000 Census report has a racial make-up of 53% White, 43% African American, 0.21% Native American, 1.55% Asian, 0.04% Pacific Islander, 0.63% from other races, and 1.68% from two or more races, and 1.28% of the population are Hispanic or Latino of any race.

NIH guidelines for the inclusion of females and minorities as subjects in clinical research will be followed. We will attempt to recruit equal numbers of each gender from each of the above racial groups. Most of our prior clinical trials achieved these gender, racial, and ethnic representations, and we expect the same for this study. We will analyze demographic data every four months and if we are failing to achieve these marks, we will increase our recruitment of the under-represented group by extending recruitment to other area clinics that include the under-represented group. There will be no exclusion of subjects based on gender, race, or ethnicity.

5. Study population source: Adolescents (ages 9-21 years) with a current DSM-IV-TR diagnosis of major depressive disorder (MDD) or Depressive Disorder NOS will be recruited from the University of Cincinnati BITREC “at-risk” cohort (n=140) of adolescent offspring of parents with bipolar I disorder.

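### The healthy-control comparison names group as its only regressor, so its standard error is too large to the extent that the matching factors predict metabolite levels

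*Combined protocol and SAP*

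**What the plan says.** Section E.b (Data Analyses), Exploratory analyses, compares baseline NAA, mI, Glu, Cho and Cr in the trial's patients with "a demographically matched subgroup of healthy control adolescents from the BITREC". The stated purpose is to establish the direction of any changes, that is, whether values normalize. Every VOI gets its own model, specified "with neurometabolite levels as the dependent variables and group (baseline at-risk adolescents with MDD vs. healthy controls) as the independent variable".

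The matching factors, the matching ratio, the subgroup size and the kind of matching (pairs or groups) are not stated. No covariate wording elsewhere reaches this model:

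- The covariates under Predictions 1 and 2 belong to the treatment comparisons.
- The clinical factors later in the exploratory paragraph, such as ADHD, are examined as effect moderators.

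On the control pool, Section F.1 says "they are recruited (n=40) already for BITREC Project 3". Section F.2 plans 60 patients. It expects about 25% to discontinue or lack usable MRS data, and calls effect sizes of 0.6 to 0.8 clinically relevant in general. The exploratory analyses carry the label "Because these exploratory analyses are hypothesis-generating secondary analyses".

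**The concern.** Matching on factors that predict the outcome makes the group difference in means less variable from sample to sample, because those factors can no longer differ much between groups. A regression with group alone does not use this. It estimates its residual variance from the full within-group spread, including the part due to the matched factors. The reported standard error then exceeds the true one, intervals are too wide and the test rejects less often than its nominal level. This is true of group matching as well as of pairing.

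Age is a plausible example, since patients range from 9 to 21 years. In Section F.4 the protocol says of younger children that "it is not possible to control for age-related differences in brain development" with the planned numbers. That sentence justifies the lower age limit. It shows that age is thought to matter for brain measures, not how strongly it predicts metabolites within 9 to 21 years.

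At stake is precision. Sections E.a and F.1 use the healthy controls to interpret whether patients' values move toward or away from normal, so a real baseline difference could be estimated with needless uncertainty.

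**Working it through.** The text available gives no power, SD or R² for this comparison, so there is no planned figure to reproduce. The check measures what the group-only model costs.

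**Inputs from the documents**
- Controls: 40 at most (F.1).
- Patients: 60 (F.2). If the whole 25% loss fell on baseline scans, 60 × 0.75 = 45. This is a worst case, because the 25% also covers later discontinuation.
- d = 0.6 and 0.8 (F.2), in units of the unadjusted within-group SD. The plan does not tie these to this comparison.
- Alpha 0.05. The plan says "we will use a standard 0.05 significance level as a threshold for interpreting interactions that may warrant further study"; applying that level to a group difference, two-sided, is an assumption.

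**Assumed**
- R², the share of within-group metabolite variance explained by the matching factors: 0 to 0.3.
- The matching achieves balance.

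**Formulas** (SD = 1)
- Reported SE, group-only: √(1/n₁ + 1/n₂)
- True SE under matching: √(1 − R²) × √(1/n₁ + 1/n₂)
- Ratio of reported to true: 1/√(1 − R²)
- True size, group-only: 2·P(Z > t_crit/√(1 − R²))
- Power, group-only: P(Z > (t_crit − d/SE_reported)/√(1 − R²)); the opposite tail is negligible
- Power, adjusted: noncentral t with noncentrality d/SE_true

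**One case in full: 40 vs 60, R² = 0.3, d = 0.6**
- Reported SE = √(1/40 + 1/60) = 0.204; √(1 − 0.3) = 0.837; true SE = 0.837 × 0.204 = 0.171.
- t_crit on 98 df = 1.984. Size = 2·P(Z > 1.984/0.837) = 2·P(Z > 2.37) = 1.8%.
- Group-only power: d/SE = 0.6/0.204 = 2.94; (1.984 − 2.94)/0.837 = −1.14; power 87.3%.
- Adjusted power: noncentrality 0.6/0.171 = 3.51; power 93.6%.
- Loss: about 6 points.

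**Across the range, 40 vs 60**

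| R² | SE ratio | Group-only vs adjusted power, d = 0.6 | Loss (points) |
|---|---|---|---|
| 0 | 1.00 | no difference | 0 |
| 0.1 | 1.05 | 84.3% vs 86.6% | 2.3 |
| 0.2 | 1.12 | 85.7% vs 90.2% | 4.5 |
| 0.3 | 1.20 | 87.3% vs 93.6% | 6.2 |

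- d = 0.8, 40 vs 60: 98.5% vs 99.1% at R² = 0.2, and 99.0% vs 99.6% at 0.3. The loss is at most 0.7 points.
- d = 0.6, 40 vs 45, R² = 0.3: 82.2% vs 90.3%, a loss of about 8 points.

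**Check by simulation** (4,000 replicates per setting, controls group-matched on age 9 to 21, 40 vs 60)
- R² = 0.3: mean reported SE 0.203 against a true sampling SD of about 0.17; type I error 2.1%; power at d = 0.6 is 86.8% group-only and 93.2% adjusted.
- R² = 0.1: reported SE 0.204 against about 0.193; type I error 3.7%; power 84.0% and 86.4%.
- R² = 0: no loss.
- Both models estimate about 0.60 for a true 0.60.
- Wrong sign: about 0.1% or less in both models at d = 0.6. At d = 0.3 and R² = 0.3 it is 4.1% group-only and 3.7% adjusted.
- Power at d = 0.3 and R² = 0.3, below the plan's relevant range: 28.5% group-only and 42.1% adjusted.

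**The case against.** The strongest reply is that little is lost. The matching does its main job at selection: it removes confounding by the matched factors, and the estimate is unbiased if balance is achieved. The analysis is exploratory and does not enter the mediation models of Predictions 4 and 5. The error is conservative, so it creates no false positives. The declared purpose is direction, which comes from the sign of the estimate. The cost also hangs on an R² that the documents do not give, for factors they do not name, and it is zero if those factors do not predict the metabolites.

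All of this stands, and it keeps the point small. It does not remove it: a wider interval than necessary is still a cost, and avoiding it needs no new data.

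The same facts rule out three stronger readings that a reader might infer.

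- *The matching is ignored and a paired analysis is required.* The plan speaks of a matched subgroup, not pairs, and 40 controls cannot be paired one to one with 60 patients.
- *Without significance, the direction reading has no basis.* The plan states no rule that makes direction depend on significance here, and the sign is practically the same under either model.
- *The loss is large.* That needs a high R², or group sizes such as 40 vs 40 or 30 vs 30. The documents support neither; no subgroup size is stated, and nothing says patients are dropped.

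**Conclusion.** The point holds as a minor one about precision. The model as written leaves out the variables used to choose the controls. If those variables predict metabolite levels, its standard errors are too large and its tests conservative. The sizes above rest on balanced matching, a two-sided 0.05 level and an R² that is assumed rather than documented. Imperfect balance would bring the test's true size back toward 5%. The finding does not extend to bias in the estimate, to the direction of the difference or to the trial's treatment and mediation analyses.

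**What to change.** In Exploratory analyses, name the matching variables and state that each VOI regression includes them, at least age and sex, as covariates beside group. Report the adjusted group difference with its 95% interval.

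This takes one sentence and no new data, since demographic matching already requires these variables in both groups. It also deals with any imbalance left after matching. The cost is a few residual degrees of freedom (98 are available with 40 vs 60 before adjustment).

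Using all 40 controls in place of a matched subgroup is an optional design choice that relies more on the age effect being modelled correctly. It is not part of this fix.

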
even the direction) of an association between two variables to depend on the levels of moderating variables. We will assess moderation by the magnitude of the interaction terms in an ANCOVA model where change in mood symptoms is the outcome and the predictors are treatment group, change in metabolite levels, and interactions between metabolite changes and treatment group. A moderated relationship would be consistent with a pattern of results where an association between metabolite levels and mood symptoms exists in the omega-3 fatty acid group, but not in the placebo group. Such an outcome is plausible because placebo response may occur due to mechanisms that are independent of those we hypothesize as causes of treatment response.

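### The exploratory predictor analysis names no dependent variable, and its key term (treatment by change in rating) does not test whether a baseline marker predicts response differently by arm

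*Combined protocol and SAP*

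**What the plan says.** The relevant text is the Exploratory analyses paragraph of section E.b (Data Analyses and Data Monitoring).

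- **The question.** Multiple regression will be used for "associations between baseline neurochemical levels and omega-3 blood levels with change in mood and behavior rating in each treatment group".
- **The key term.** The next sentence reads: "The treatment by change in rating scale interaction term will be the primary measure of interest". The dependent variable is not named.
- **The decision rule.** For the exploratory work, "we will use a standard 0.05 significance level as a threshold for interpreting interactions that may warrant further study".
- **Related models.** The missing-data sensitivity analyses in the same paragraph are described as applying "in regression analyses where change in mood symptom rating is predicted from change in a neurophysiologic and biological measure". The moderation model that closes the paragraph has change in mood symptoms as the outcome, and its moderation terms are "interactions between metabolite changes and treatment group".
- **Numbers.** Section F.2: "We propose to randomize 30 subjects per treatment group, for a total of 60 subjects". It also expects that "approximately 25% of patients will either discontinue study participation prior to completing study procedures or will not have usable MRS data".

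**The concern.** The natural question is whether a marker measured before treatment predicts change in rating differently under omega-3 than under placebo. The term that answers it is treatment by baseline marker, in a model with change in rating as the outcome. The plan names a different interaction, and one analyst could reasonably fit a different model from another.

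Nothing else in the Data Analyses section fills the gap. The closing moderation model concerns *changes* in metabolites, not baseline levels, and the other sentence on effect moderators concerns clinical factors such as ADHD.

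At stake is which baseline markers are taken forward as possible predictors of response, because the 0.05 threshold is applied to interactions of this kind.

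**Working it through.** **1. Nothing to reproduce.** The plan gives no power, slope, SD or error rate for this analysis. The check concerns what the named term tests.

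**2. Change in rating as outcome.** The term is treatment × change in rating, so the outcome would appear among its own predictors. The model has no useful meaning.

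**3. Baseline marker as outcome.** Let X be the marker, scaled to SD 1, with the same distribution in both arms because of randomization. In arm t, let change in rating be a_t + b_t·X + error, with residual SD s_t. Then

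- the slope of change on marker (the quantity of interest) is b_t;
- the slope of marker on change is Cov(X, change)/Var(change) = b_t/(b_t² + s_t²).

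The named interaction therefore compares b/(b² + s²) between arms, not b.

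**4. Inputs.**

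- From the plan: 30 per arm; 25% loss, so 30 × 0.75 = 22.5, taken as 22 per arm; threshold 0.05.
- Assumed: a two-sided test, all slopes and all residual SDs.
- Method: ordinary least squares on simulated trials, 20,000 per row. The correct model is change ~ treatment + X + treatment × X. The reversed model is X ~ treatment + change + treatment × change. Repeat runs differed by a point or two.

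**5. Reversed slopes by hand.**

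- Slopes 0.5 in both arms. SD 1.0: 0.5/(0.25 + 1) = 0.400. SD 0.85: 0.5/(0.25 + 0.7225) = 0.514. SD 0.7: 0.5/(0.25 + 0.49) = 0.676. SD 0.5: 0.5/(0.25 + 0.25) = 1.000. Equal true slopes become unequal.
- Slopes 0.5 v 1.0, SD 0.71 (variance 0.5) in both arms: 0.5/(0.25 + 0.5) = 0.667 and 1.0/(1 + 0.5) = 0.667. Unequal true slopes become equal.
- Slopes 0.2 v 0.8, SD 1.3 v 0.6: 0.2/(0.04 + 1.69) = 0.116 and 0.8/(0.64 + 0.36) = 0.800. The gap widens from 0.6 to 0.684.

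**6. Rejection rates at 0.05.**

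| Slopes | Residual SDs | Moderation? | Correct, 22/arm | Reversed, 22/arm | Correct, 30/arm | Reversed, 30/arm |
|---|---|---|---|---|---|---|
| 0, 0 | 1.0 v 0.5 | no | 5% | 5% | 5% | 5% |
| 0.5, 0.5 | 1.0 v 1.0 | no | 5% | 5% | 5% | 5% |
| 0.5, 0.5 | 1.0 v 0.85 | no | 5% | 7% | 5% | 8% |
| 0.5, 0.5 | 1.0 v 0.7 | no | 5% | 16% | 5% | 21% |
| 0.5, 0.5 | 1.0 v 0.5 | no | 5% | 50% | 5% | 64% |
| 0.5, 1.0 | 0.71 v 0.71 | yes | 58% | 6% | 73% | 6% |
| 0.2, 0.8 | 0.6 v 1.3 | yes | 45% | 8% | 58% | 9% |
| 0.2, 0.8 | 1.3 v 0.6 | yes | 45% | 82% | 58% | 93% |

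The correct term keeps its 5% level in every row without moderation. The reversed term keeps it in the first two rows only.

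**The case against.** **It may be a slip of wording.** The plan treats change in mood as the outcome in neighbouring text. A statistician who does the same here would find that the named term cannot be used and would probably replace it with treatment × baseline marker. The error rates above would then never arise. This stands as a possibility. It is not certain: the healthy-control comparison just before this sentence does make metabolite levels the dependent variable, so a reversed fit is not far-fetched.

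**A reader might infer that the plan has specified a reversed regression.** The documents do not support that. They leave the dependent variable open; the reversed fit is only the orientation in which the named term can be estimated.

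**A reader might infer that the two tests agree only if the arms have equal spread.** That is false. With no association in either arm, both reject about 5% of the time even with SDs of 1.0 v 0.5. Equal residual SDs are also not enough when the slopes differ, as the sixth row shows.

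**The size depends on chosen inputs.** This stands. With a mild SD difference the excess is small (7% against 5%), and the direction of the power error depends on which arm has the larger residual SD.

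**The consequence is limited.** This also stands. The plan labels these analyses secondary and hypothesis-generating.

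**Conclusion.** The concern holds in a limited form. The dependent variable is unstated, and the named interaction does not answer the stated question under either reading: it is unusable if change in rating is the outcome, and it tests a different quantity if the marker is.

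The size applies only if the reversed model is fitted, and it rests on assumed slopes and SDs. Under those assumptions, the result ranges from no harm (both slopes zero, or slopes and residual SDs equal in both arms) to a false-flag rate of one in two, and from nearly complete loss of power to overstated evidence of moderation. The problem persists at the 22 per arm expected after losses.

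It would be wrong to infer that the efficacy, safety or mediation results are at risk. Predictions 1 to 5 do not use this term. The effect is confined to which baseline markers are reported as candidate predictors of response.

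**What to change.** Replace the sentence that names the key term with:

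> Change in rating will be the dependent variable, with treatment, baseline marker and treatment × baseline marker as predictors; the treatment × baseline marker term is the measure of interest.

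This brings the analysis into line with the moderation model at the end of the same paragraph. Adding the baseline rating as a covariate is optional and is not part of the correction.

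The cost is one sentence of analysis-plan wording. Data, visits, sample size and software are unchanged.
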